1.0 Objectives

1.1 Primary Objective

- 1.1.1 To determine the efficacy of the Levonorgestrel Intrauterine Device (IUD) to treat complex atypical hyperplasia (CAH) and grade 1 endometrioid endometrial carcinoma (G1 EEC).
- 1.1.2 To determine if response to therapy can be predicted based on the molecular profile of the tumor or by change in gene expression after therapy.

1.2 Secondary Objectives

- 1.2.1 To assess quality of life outcomes in patients treated with Levonorgestrel IUD.
- 1.2.2 To document the toxicity profile of the Levonorgestrel IUD in the treatment of complex atypical hyperplasia and grade 1 endometrioid endometrial cancer.
- 1.2.3 To evaluate the molecular profile of the hysterectomy specimen of patients treated with the Levonorgestrel IUD. Compare molecular profile in pretreatment tissue to hysterectomy tissue between responders and non-responders to Levonorgestrel IUD therapy.
- 1.2.4 To evaluate long-term survival, disease status, and fertility outcomes in patients with Levonorgestrel IUD.

2.0 Background

2.1 Endometrial Carcinoma and Complex Atypical Hyperplasia

Endometrial cancer is the most common gynecologic cancer in the United States. The American

Cancer Society estimates that in 2007 there will be 39,080 new cases and 7,400 deaths from this disease[1]. The standard of care for early grade disease is complete surgical resection[2].

However, this may not be the preferred option in young women who have not completed childbearing. Furthermore, women with endometrial carcinoma may be suboptimal surgical candidates secondary to the presence of morbid obesity and multiple co-morbid conditions. This stems from the fact that these health conditions and endometrial cancer share many risk factors[3].

Complex atypical hyperplasia (CAH) is a precursor lesion to the most common histology of endometrial carcinoma, endometrioid type. In fact, in a study of 170 women with untreated endometrial hyperplasia, 29% of CAH progressed to endometrial carcinoma[4]. Trimble et al demonstrated that 42% of women with CAH on endometrial biopsy had a concurrent diagnosis of endometrial carcinoma on their subsequent hysterectomy specimen[5]. These data indicate that the two conditions are closely related, and often may be present together.

Furthermore, the initial diagnosis of CAH versus grade 1 endometrioid endometrial carcinoma (G1EEC) can be difficult to make. In the Trimble study, three gynecologic pathologists were unable to reach a consensus diagnosis in 16 of 289 endometrial biopsy specimens. Of those patients, 10 had carcinoma on their hysterectomy specimen[5]. An assessment of the reproducibility of CAH diagnosis in the setting of a Gynecologic Oncology Group trial revealed only 38% agreement with the initial diagnosis of CAH by a consensus panel. 30% of the biopsies with incorrect diagnoses were noted to be adenocarcinoma[6]. Given their close association and the difficulties in distinguishing between the two diagnoses, the inclusion of both entities in a treatment trial is reasonable.

2.2 Rationale

One of the most well-established risk factors for the development of CAH and endometrial

carcinoma is exposure to unopposed estrogen. In fact, a majority of the key conditions associated with endometrial cancer are directly or indirectly related to estrogen. Progesterone is known to counteract the effects of estrogen in the endometrium, thus, it has been used as a primary therapy for CAH and as an alternative primary therapy or adjuvant therapy for endometrial cancer[2].

Progesterone has been demonstrated to be an acceptable and efficacious option for treatment of complex atypical hyperplasia and grade 1 endometrioid endometrial carcinoma[3,7]. Despite the success of progesterone treatment, many women do not tolerate the side effects of systemic progesterone or are unable to maintain compliance with this therapy[8]. Montz et al evaluated the use of a progesterone releasing intrauterine device (Progestesert) to treat stage 1a, grade 1 endometrioid endometrial carcinoma. They demonstrated complete regression of G1EEC in 7 of 11 patients at 6 months and in 6 of 8 patients at 12 months[9]. Unfortunately, this therapy is no longer available for therapeutic use. The Levonorgestrel Intrauterine Device (LIUD) has been demonstrated to provide a consistent dose of progesterone to the uterine cavity with minimal systemic effects[10]. The toxicity of this treatment is low, with the most common complications consisting of irregular bleeding, expulsion, or uterine perforation during placement[11].

The studies of the LIUD for complex atypical endometrial hyperplasia are promising, but have been limited by low numbers. In a study of endometrial hyperplasia, there was regression of disease in 100% patients (n=26) treated with the LIUD compared to only 55% of patients treated with oral progesterone. It is important to note that only two of the patients in this study had CAH[12]. Wildemeersch et al noted 100% regression after Mirena placement in the eight patients with complex atypical hyperplasia in their study[13].

The use of the Mirena for the treatment of grade 1 endometrioid endometrial carcinoma has been less well studied, with only a few cases documented in the literature. Giannopoulos et al reported complete regression of a well-differentiated endometrial carcinoma after treatment with the LIUD[14]. Other case series, however, have had lower rates of success. Bahamontes et al treated two women with morbid obesity and G1EEC with the Mirena while awaiting gastroplasty for weight reduction. Both women had residual G1EEC in their hysterectomy specimens after 6 and 7 months, respectively[15,16]. In a case series of four women with G1EEC treated with LIUD, only one woman had complete regression at 6 months[16]. A larger study is necessary to clarify if the LIUD is effective in the treatment of grade 1 endometrioid endometrial carcinoma.

Given the success of oral progesterone for the treatment of both conditions, the LIUD is a rational option for patients with CAH and grade 1 endometrioid endometrial carcinoma. However, the existing literature is conflicting regarding the success of this treatment. Therefore, we propose a phase II trial to assess the efficacy of the LIUD for treatment of complex atypical hyperplasia or Grade 1 endometrioid carcinoma. Patients will receive this treatment for one year, as the median time to complete regression of G1 EEC during oral progesterone therapy is generally 12 weeks, with a range of 4 – 60 weeks[3].

2.3 Correlative Studies

In an earlier study, we discovered a cadre of genes which were highly induced in the endometrium of postmenopausal women after 3 months of treatment with estrogen therapy. These included PR, EIG121, IGF-I, RALDH2, sFRP1, and sFRP4[17]. Given that estrogen excess is a key factor in the development of hyperplasia and endometrioid type endometrial carcinoma, we subsequently studied the expression of these genes in a cohort of endometrial carcinoma patients. We found that G1EEC demonstrates high expression of these estrogen-induced genes[17]. Given the antagonistic effect of progesterone, these genes should be down-regulated after progesterone treatment.

Additionally, McCampbell et al demonstrated a step-wise increase in IGF-IR expression along the continuum from normal endometrium to G1EEC[18]. Our data confirmed that IGF-IR was highly

expressed in G1EEC, but had decreasing expression with increasing grade[17]. As this protein is known to be involved in an estrogen-regulated endometrial proliferation pathway, it is a rational target to include in our mRNA analysis. We plan to perform quantitative real time reverse transcriptase polymerase chain reaction for the aforementioned genes in the pre-treatment D&C specimen and 3-month post-treatment biopsy. These studies will provide pharmacodynamic evidence that the LIUD is having an effect on the endometrium. This time frame is based on results from our NCI-funded study of chemoprevention in patients with Lynch Syndrome without endometrial disease, which demonstrated a change in biomarker expression after three months treatment with progesterone-based therapy[19].

In 2007, we found that loss of PTEN and activation of mTOR were associated with poor response to progesterone in a murine hyperplasia model[20]. Given the need for markers which predict response to therapy in these patients, we will perform immunohistochemistry for PTEN and phosphorylated mTOR on paraffin-embedded tumor specimens.

3.0 Background Drug Information

Levonorgestrel Intrauterine Device (Mirena)

3.1 Description[11]

The Mirena releases a consistent dose of progesterone to the uterine cavity for five years. Its primary indication is contraception.

3.2 Mechanism of Action[11]

The Mirena releases 20 μ g of levonorgestrel into the uterine cavity daily for five years. Levonorgestrel is bound primarily in the serum to proteins and is metabolized into a large number of inactive metabolites. Metabolic clearance rates may differ among individuals by several-fold. The elimination half-life of the oral form is approximately 17 hours. Both levonorgestrel and its primary metabolites are excreted primarily in the urine. It causes local progestogenic effects in the uterine cavity. Morphological changes of the endometrium are observed, including stromal pseudodecidualization, glandular atrophy, leukocytic infiltration and a decrease in glandular and stromal mitosis. Mirena provides effective contraception in 99.3% of women over a five-year span.

3.3 Drug Supply[11]

Mirena is commercially available. There will be no charge to the patient or their insurance company for the Mirena IUD. It will be provided free of charge as part of the study.

3.4 Storage[11]

Mirena can be stored at 25°C, but can tolerate temperatures between 15° – 30°C for short time periods. It should remain in its sterile package until use.

3.5 Preparation and Administration[11]

The Mirena consists of a T-shaped polyethylene frame with a steroid reservoir around the vertical stem. The reservoir consists of a cylinder, made of a mixture of levonorgestrel and silicone and is covered by a silicone membrane. It contains a total of 52 mg of levonorgestrel. A monofilament brown polyethylene removal thread is attached to a loop at the end of the vertical stem of the body.

3.6 Toxicity Data[11]

The most serious adverse events are ectopic pregnancy (1/1000), sepsis (4 cases of Group A Streptococcus in 1999), and pelvic inflammatory disease. Other complications reported include irregular bleeding, embedment in the uterus, perforation of the uterus and ovarian cysts. Minor adverse reactions seen in more than 5% of subjects include abdominal pain, leukorrhea, headache, vaginitis, back pain, breast pain, acne, depression, hypertension, upper respiratory

infection, nausea, nervousness, dysmenorrhea, weight increase, skin disorder, decreased libido, abnormal pap smear and sinusitis.

4.0 Patient Eligibility

4.1 Inclusion Criteria

4.1.1 All patients with a diagnosis of complex atypical hyperplasia or endometrial biopsy within three months of study enrollment OR patients with a diagnosis of grade 1 endometrioid endometrial carcinoma on endometrial biopsy within three months of study enrollment in the presence of one or more of the following:

- desire for future fertility
- morbid obesity (body mass index > 40)
- multiple co-morbidities (ASA Class 3 or 4)

4.1.2 No prior treatment for diagnoses 4.1.1

4.1.3 Women of any racial or ethnic group.

4.1.4 Ability to comply with endometrial biopsies every 3 months

4.1.5 Willing and able to sign informed consent.

4.1.6 Age greater than 18 years.

4.2 Exclusion Criteria

4.2.1 Diagnosis of grade 1 endometrioid endometrial carcinoma without the presence of one of the 3 criteria mentioned in 4.1.1.

4.2.2 Diagnosis of grade 2 endometrioid endometrial carcinoma or higher on endometrial biopsy or on dilation and curettage specimen.

4.2.3 Evidence of extrauterine spread of disease on imaging or during surgical evaluation.

4.2.4 Congenital or acquired uterine anomaly which distorts the uterine cavity.

4.2.5 Acute pelvic inflammatory disease.

4.2.6 Acute liver disease or previously diagnosed liver tumor (benign or malignant).

4.2.7 Conditions associated with increased susceptibility to infections with microorganisms. Such conditions include, but are not limited to, AIDS, leukemia and IV drug abuse.

4.2.8 Genital actinomycosis.

4.2.9 Current carcinoma of the breast.

4.2.10 Current pregnancy.

4.2.11 Breastfeeding mothers.

5.0 Treatment Plan

5.1 Study Design

This study will be a Bayesian phase II, single arm clinical trial. The study will enroll up to 50 evaluable patients. All women with the diagnosis of CAH on endometrial biopsy will be eligible. Women with G1 EEC on endometrial biopsy will be eligible if they desire fertility sparing options, are morbidly obese (BMI >40), or have co-morbid conditions which preclude a major surgical procedure (ASA Class 3 or 4).

5.2 Patient Accrual

All eligible patients being seen at The University of Texas M. D. Anderson Cancer Center Department of Gynecologic Oncology will be identified from a list generated by the clinic. Their primary physician will be contacted and asked permission to contact the patient for discussion of the trial. All Gynecologic Oncology physicians, registered nurses, advanced practice nurses and clinical fellows will be made aware of the trial through presentations, meetings, and fliers in the clinic. Benign gynecologists within the department will also be made aware of the trial through the same mechanisms.

In addition, the trial will be opened at the MD Anderson Cancer Center Regional Care Centers and the Harris Health System (Lyndon B. Johnson General Hospital). Finally, local Houston

benign gynecologists will be informed of the trial through presentations and fliers, and will be asked to refer patients they feel are eligible for participation.

5.3 Pretreatment Evaluation

After signing the informed consent, the patients will follow one of two treatment plans depending on their initial biopsy diagnosis. All patients will undergo a urine pregnancy test (women of child bearing potential) and cervical cultures in clinic to rule out pregnancy and active cervical infection. Patients with G1 EEC will undergo clinical staging procedures including chest radiography and MRI of the abdomen and pelvis. This will be a routine MRI of the abdomen and pelvis with standard pulse sequences including dynamic gadolinium enhanced imaging of the uterus.

Women who are unable to undergo MRI due to morbid obesity or other contraindication will have a CT scan of the abdomen and pelvis and transvaginal ultrasound. For those patients who are unable to undergo CT due to morbid obesity, transvaginal ultrasound will be performed. Scans will be reviewed by the diagnostic radiology collaborator on the study. Women will be excluded if there is evidence of extrauterine spread of disease.

Both cohorts of patients (CAH and G1 EEC) will then undergo an exam under anesthesia (EUA) and a dilation and curettage (D&C) in the operating room to sample the entire endometrium. This specimen will be read by a certified gynecologic pathologist at our institution and report dictated in the electronic medical record. At the time of D&C, the LIUD will be placed. Women who have previously undergone D&C for this diagnosis will not be required to undergo a second D&C. The pathology specimen will be obtained for review and confirmation of diagnosis and for the correlative studies to be performed. The LIUD will then be placed in the clinic setting.

If patients with an initial diagnosis of CAH are upgraded to G1 EEC, they will be assessed for eligibility through inclusion criteria 1. If the patient does not meet inclusion criteria, they will be removed from the study. Otherwise, they will undergo chest radiography, and MRI of the abdomen and pelvis and/or CT of the abdomen and pelvis and/or transvaginal ultrasound as detailed above in the post-operative period. Women will remain on study if they have confirmed CAH and/or G1 EEC on the D&C specimen and have no evidence of extrauterine spread of disease. If a woman is excluded from the trial after LIUD is placed, the LIUD will be subsequently removed. Removal of the LIUD can be performed in the operating room if the patient proceeds with surgical treatment or in the clinic.

5.4 Evaluation During Study

All subjects will be evaluated at one month (+/- 1 week) after LIUD placement to confirm the placement of the LIUD. This visit may be performed at MD Anderson or at the subject's local physician office, based on patient preference. Placement will be confirmed by speculum exam and, if necessary, using pelvic ultrasound.

Endometrial biopsy may be performed while the LIUD is left in situ. The endometrial biopsy will be performed with the Pipelle endometrial suction instrument (Cooper Surgical, Trumbull, CT). Each patient will have a follow-up endometrial biopsy every three months for one year (+/- 2 weeks). Endometrial evaluation every three months is the standard of care for patients with CAH or G1EEC undergoing conservative therapy. The pathology of the endometrial biopsies will be read by a certified gynecologic oncologist and report dictated in the electronic medical record.

The molecular profile of the endometrial lesion in the pre-treatment D&C specimen and 3-month post treatment biopsy will be determined. Using formalin-fixed, paraffin-embedded tissue, the mRNA expression profile will be determined by real time reverse transcriptase polymerase chain reaction for a panel of genes including PR, EIG121, IGF-I, IGF-IR, RALDH2, sFRP1, and sFRP4. The level of mRNA expression will be normalized by comparison to the expression of α -actin and 18S, two cellular housekeeping genes. See Appendix D for RT-PCR protocol. Protein expression

of PTEN and phosphorylated mTOR will be determined through the performance of immunohistochemistry on the formalin-fixed, paraffin-embedded endometrial biopsy specimens. See Appendix E for the immunohistochemistry protocol.

An evaluation of any complications related to the LIUD will be completed at each follow-up visit by study personnel. This assessment can be found in Appendix F. It includes concerns which are specific to the LIUD as well as typical side effects of systemic progesterone therapy. In addition, the patient will be given a diary to fill out at home during the first 3 months after LIUD placement. This diary is provided by Bayer and monitors vaginal bleeding after LIUD placement. See Appendix I for this diary.

Finally, quality of life assessment will be performed at baseline and at each 3 month follow-up visit using the SF-36 instrument (Appendix G). This 36-question validated instrument is a generic measure which incorporates an 8-scale profile of functional health and well-being scores as well as psychometrically-based physical and mental health summary measures and a preference-based health utility index. These results will be compared to available standardized results from this instrument. This is intended to provide pilot data for future trials including the LIUD.

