5.5 Criterion for Response

Response is defined as follows:

Complete response is defined as no endometrial abnormality or the presence of endometrial hyperplasia without cytologic atypia at the one year time point.

Partial response is defined as the presence of complex endometrial hyperplasia with cytologic atypia in patients with an initial diagnosis of grade 1 endometrial cancer, at the one year time point.

Stable disease is defined as no change in diagnosis at the one year time point.

Progressive disease is the presence of grade 2 cancer or above in patients with an initial diagnosis of grade 1 cancer OR presence of grade 1 cancer or above in patients with an initial diagnosis of complex atypical hyperplasia at any time point.

Patients with stable disease or progressive disease will be categorized as non-responders for the purposes of molecular analysis.

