6.1.2 Handling of Sample

6.1.2.1 Dilation and Curettage and Three-Month Endometrial Biopsy

A hematoxylin and eosin slide will be prepared for the gynecologic pathologist to read and obtain diagnosis. The remainder of the tissue will be divided for PCR and IHC. RNA extraction will be performed on the tissue and the resultant RNA will be stored in the -80°C refrigerator until analysis.

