7.3 Endpoints

The primary outcome will be response to therapy, which is defined as complete response or partial response (detailed in section 5.5), assessed at the one year endometrial biopsy. Secondary outcomes will include toxicity and complication information. The molecular profile will be utilized to determine if response to therapy can be predicted. Additionally, toxicity assessment and quality of life assessment with the SF-36 survey will be performed at baseline and at each 3-month follow up visit as described in Section 5.4.

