8.0 Data and Protocol Management

This study is planned as a multi-site study. All patients will be centrally registered into the Clinical Oncology Research System (CORe) at M. D. Anderson Cancer Center. Information will include a completed eligibility check list, patient name, date of birth, consent date, and race. Once accrual is complete, study data will be combined for analysis.

Protocol Compliance: The study research nurse will be present at each visit to ensure compliance with protocol guidelines. Decisions for removal from study based on response will be made by the Study Chairman and the Study Pathologist ([name]).

Data Entry: Data must be entered into the Gyn Oncology Departmental database for this protocol.

Accuracy of Data Collection: The Study Chairman will be the final arbiter of response or toxicity should a difference of opinion exist.

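### Section 5.4 has a gynecologic oncologist read the endpoint biopsies, in conflict with 5.3 and 6.0, and 8.0 lets the Study Chairman settle disputes over a purely histologic response

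*Combined protocol and SAP*

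**What the plan says.** **Endpoint.** Section 7.3 defines the primary outcome as complete or partial response, "assessed at the one year endometrial biopsy". Section 5.5 defines each category by histology, for example: "Complete response is defined as no endometrial abnormality or the presence of endometrial hyperplasia without cytologic atypia at the one year time point".

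**Readers.** For the baseline curettage, section 5.3 says: "This specimen will be read by a certified gynecologic pathologist at our institution and report dictated in the electronic medical record". For the three-monthly follow-up biopsies, section 5.4 says: "The pathology of the endometrial biopsies will be read by a certified gynecologic oncologist and report dictated in the electronic medical record". Sections 6.1.2 and 6.2.2 each cover both the curettage and the 3-month biopsy, and both say: "A hematoxylin and eosin slide will be prepared for the gynecologic pathologist to read and obtain diagnosis".

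**Disputes.** Section 8.0 has the Study Chairman and the Study Pathologist decide together on removals based on response. Under accuracy of data collection it then adds: "The Study Chairman will be the final arbiter of response or toxicity should a difference of opinion exist".

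The plan describes no independent, central or masked reading of the one-year biopsy.

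**The concern.** There are two separate problems.

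First, the plan names two different specialties for reading follow-up tissue. For the biopsy that carries the primary endpoint, the only instruction names the specialty that does not appear at baseline. Response compares a follow-up diagnosis with a baseline diagnosis, so the two should be made by the same kind of reader under the same criteria.

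Second, as 8.0 is worded, the person who leads the trial can have the last word over a pathologist on what a slide shows. The trial is open, has no control arm and relies on a success rate against a fixed 65% goal. Any shift in how slides are classified goes straight into that rate, with no comparison group in which it could cancel.

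**Working it through.** **1. Who reads which specimen**

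| Specimen | 5.3 | 5.4 | 6.1.2 and 6.2.2 |
|---|---|---|---|
| Baseline curettage | gynecologic pathologist | – | gynecologic pathologist |
| 3-month biopsy | – | gynecologic oncologist | gynecologic pathologist |
| 6- and 9-month biopsies | – | gynecologic oncologist | – |
| 12-month biopsy (endpoint) | – | gynecologic oncologist | – |

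The 3-month row is a direct contradiction. In the last two rows 5.4 stands alone, so nothing elsewhere overrides it for the endpoint biopsy.

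**2. Who settles a dispute**

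Every category in 5.5 is a histologic finding, so a dispute over response is normally a dispute over a slide. Section 8.0 gives the Study Pathologist a joint role in removals based on response, but no stated role in reading the one-year biopsy or resolving disagreement about it. Final authority rests with the Study Chairman alone.

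**3. What the plan's own reproducibility figures bear on**

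Section 2.1 reports that three specialist pathologists reached no consensus in 16 of 289 biopsies (16/289 = 5.5%), and that a consensus panel agreed with 38% of initial CAH diagnoses. Section 2.1 uses both to show that CAH and G1 EEC are hard to tell apart on diagnostic biopsies. Under 5.5, that distinction at one year has these effects:

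| Baseline | Read as CAH at one year | Read as G1 EEC at one year |
|---|---|---|
| CAH | stable: not a response | progressive: not a response |
| G1 EEC | partial response: a response under 7.3 | stable: not a response |

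At the one-year biopsy it therefore changes the 7.3 endpoint only through partial response in G1 EEC patients. It does not change the count of complete remissions used in the examples of 7.2 and 7.4. Before one year, a G1 EEC reading in a CAH patient counts as progression and takes her off study (5.5, 5.6), so the reader of the interim biopsies matters too.

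**4. Scale of one patient**

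Inputs are the Beta(1.3, 0.7) prior (7.2), n = 50 and the 90% credible interval (7.4). With x successes the posterior is Beta(1.3 + x, 0.7 + n − x), and the interval runs from its 5th to its 95th percentile.

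- Plan's figures: 27/50 gives Beta(28.3, 23.7), 43.1% to 65.6%; 35/50 gives Beta(36.3, 15.7), 59.0% to 79.7%. Both match 7.4.
- One success fewer: 26/50 gives Beta(27.3, 24.7), 41.1% to 63.7%.

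The 7.4 rule drops the intervention if the upper bound is below 65%, so 26/50 fails and 27/50 is not ruled out. If the 7.2 rule is applied after every patient, a trial with 26 or fewer of 49 has already stopped, and the same one-patient step appears there as 26/49 against 27/49.

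**5. Illustration with assumed misreading rates**

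The documents give no such rates. Let p be the true success rate, m the share of responders read as non-responders, and f the share of non-responders read as responders. The observed rate is p(1 − m) + (1 − p)f. Early-stop probabilities come from an exact recursion on the listed boundaries, checked after each patient from 20 to 49. Table 1 is closely reproduced: 0.799 against a stated 0.793 at 50%, and 0.132 against 0.133 at 65%.

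| p | m | f | Observed rate | Early-stop probability |
|---|---|---|---|---|
| 0.50 | 0 | 0 | 0.50 | 0.80 |
| 0.50 | 0 | 0.10 | 0.50 + 0.05 = 0.55 | 0.57 |
| 0.50 | 0 | 0.20 | 0.50 + 0.10 = 0.60 | 0.32 |
| 0.50 | 0.10 | 0.10 | 0.45 + 0.05 = 0.50 | 0.80 |
| 0.65 | 0 | 0 | 0.65 | 0.13 |
| 0.65 | 0.10 | 0 | 0.585 | 0.39 |

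One-sided misreading matters in either direction. Balanced misreading at p = 0.50 leaves the observed rate unchanged. Nothing in the documents says which case would apply.

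**The case against.** The strongest reply on the reader is that 5.4 contains a one-word slip. Its sentence closely mirrors the one in 5.3, and 6.1.2 and 6.2.2 already send a follow-up biopsy to the gynecologic pathologist. This stands as far as it goes. A reader might infer that the trial deliberately has baseline and outcome read by different specialties, but the documents contradict each other and do not support that. The slip would still be the only instruction for the endpoint biopsy, so it needs correcting.

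On arbitration, the reply is that the sentence in 8.0 applies only when opinions differ, covers response and toxicity together, does not say that the Study Chairman re-reads slides, and follows a sentence giving the Study Pathologist a share in removal decisions. All of that is true. It does not alter the effect of the wording, which lets the Study Chairman overrule a pathologist on a histologic diagnosis.

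On size, two stronger readings are tempting. A reader might take the 5.5% non-consensus rate, multiply by 50 to get 2.8, and conclude that about 3 patients, or 6 percentage points, would go to arbitration. The documents do not support this: that rate describes three specialists reading diagnostic biopsies, not one-year biopsies on treatment for which 5.4 describes a single reader, and 6 points would require every dispute to fall the same way. A reader might also infer drift towards a reading of no atypia. The figures in 2.1 concern CAH against G1 EEC, a different boundary, and no error rate or direction for atypia is given. Finally, a one-patient step exists at any discrete boundary and is not evidence of bias.

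**Conclusion.** The point holds as an inconsistency about who reads the follow-up biopsies, together with a weakness in who settles disputed responses. Both should be corrected because they concern the primary endpoint. Correcting the word in 5.4 does not resolve the arbitration sentence in 8.0.

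The size of any reading bias cannot be computed from the documents. The 26/50 against 27/50 comparison shows only how little reclassification is needed at the decision point. The early-stop probabilities under misreading rest on assumed rates of 10% to 20% and are not estimates. The conclusion rests on the wording of 5.3, 5.4, 5.5, 6.1.2, 6.2.2, 7.3 and 8.0, not on those figures.

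**What to change.** - **Section 5.4:** name a certified gynecologic pathologist as reader of the follow-up biopsies, in line with 5.3 and 6.0.
- **Section 8.0:** make the Study Pathologist, already named there, the final arbiter of histologic response, and limit the Study Chairman's arbitration to toxicity.
- **Optional:** where practical, have disputed slides read without knowledge of the clinical course. The gain is limited. The tissue effects of the device listed in 3.2 may reveal that a slide is on-treatment, and masking disputed slides leaves undisputed readings unmasked. The two changes above do not depend on it.

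The cost is two sentences, with no extra visit, sample or patient. There is one small downside. The documents do not say whether the Study Pathologist is also the primary reader; if so, a dispute over that reading would be settled by the same person, and independence in those cases would need a second gynecologic pathologist.
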